To ensure balance of intervention groups by food security status, we will use stratified randomization to allocate subjects to usual care or CRx-H. Randomization within each strata, immediately after enrollment, will be facilitated by biostatistician [name], using the method of permuted blocks and the uniform random number function in Stata Version 15. A stratum will be closed for enrollment once its accrual goal has been reached.

(1) Usual Care Arm: the usual care arm will receive information in the standard “Caregiver FYI Admissions Packet” from hospital admission staff about all available retail food options in the hospital and the self-serve food pantries operated by Feed1st. In addition to food resources, this packet includes information about visiting hours, parking, hospital amenities, safety restrictions, and patient/caregiver rights and responsibilities. The Feed1st pantries are listed as a food resource for families in need of “free, nutritious food items.” Signage in the Feed1st pantries include information about the Community Resource Navigator (the navigator). Usual care also includes referral to social work according to the discretion of the healthcare team.

(2) CommunityRx-Hunger (CRxH): In this arm of the study, caregivers will receive CRxH in addition to usual care. CRxH will be initiated by the navigator as part of the discharge process and will include: (a) a brief, structured educational intervention about the common problem of food insecurity in households with children and co-occurring needs, like housing, legal and financial assistance, and transportation, (b) delivery and review of a HealtheRx for nearby, vetted resources to address these needs (SNAP/WIC enrollment, food support, services to meet other basic needs), and (c) coaching on how to activate community resources and the community resource navigator, including a series of automated text messages.

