We will conduct two waves of baseline and 1 week follow-up pre-testing (Y1Q2), each with 5 food secure and 5 food insecure subjects (20 total) to ensure survey quality and minimize risk of measurement and CAPI error. The baseline survey will query domains, including: facilitators and barriers (e.g., household composition, SNAP/WIC enrollment, stigma due to racial discrimination), proximal outcomes (e.g. knowledge and use of food, SNAP/WIC and other self-care resources, and communication with members of the child’s healthcare team) and distal outcomes (e.g. caregiver self-efficacy, satisfaction with care, health and healthcare outcomes). Dynamic factors will be assessed at appropriate intervals.

Food security status will be measured during the study screening process by the validated 12-month recall 18-item Household Food Security Survey (HFSS) (score of <3, food secure versus score ≥ 3 , food insecure). Severity of adult and child food insecurity at 12 months (secondary outcome), will be derived from the 18-item HFSS (primarily using the continuous score but also employing the categories defined by the USDA and also validated for severity of food insecurity). At baseline, we will assess food security in the past 12 months and past 30 days to better understand patterns of food insecurity in the immediate pre-hospitalization period. We will assess food security at 1 week using open-ended questions and at 30, 90 and 180 days using the 30-day recall 18-item HFSS to assess change over time. At 12 months, we will again assess food security using both 12 month and 30 day recall to elicit a full picture of food security since study enrollment.

The primary outcome for Aim 1, caregiver self-efficacy, will be assessed using the same measure that we used in the CRx trial. Developed using Bandura’s Self-Efficacy Scale, we will ask “How confident are you in your ability to find resources in your community that help you manage your health?” Responses will be assessed on a 5-

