The main analyses will follow the principle of intent-to-treat, and include all 480 food insecure caregivers in the study arm to which they were allocated. We aim to minimize missing data by employing interviewer-administered surveys and communicating to participants the protections of a certificate of confidentiality. Using these strategies, item non-response ranged from 0-3% in our CRx trial. To avoid potential bias due to missing data, analyses will be conducted using multiple imputation with the chained equations method or inverse probability weighting to account for dropout and/or item non-response. In addition, characteristics of caregivers who complete each interview will be compared to caregivers who do not.

To fully leverage the longitudinal data, generalized linear mixed-effects models (GLMM) will be fit with particular interest in the time (baseline and 7, 30, 90 and 180 days and 12 months post-discharge) by study arm interaction. Based on this model, appropriate contrasts to test the intervention effect at specific time points (e.g., 12 months) will be constructed. These contrasts will permit examination of early versus late effects of the intervention, valuable information for future iterations of this and other parent/caregiver self- and family management interventions. GLMM can be used for continuous (e.g., food security score, amount of fruits and vegetables per day), ordinal (e.g., caregiver self-efficacy, food insecurity categories), or binary (e.g., enrollment in SNAP/WIC) outcomes. If there is a serious imbalance in baseline covariates despite randomization, those covariates will be included in the model. Latent growth curve modeling is a viable alternative to GLMM and will be explored when sufficient variability in the distributions of patterns of outcomes by time points exist (e.g., with the binary outcomes there will be a limited number of potential patterns).

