We will also use survival analysis methods and methods for analyzing count data (e.g., Poisson or negative binomial regression) to assess the following secondary outcomes among children: 1) time to child follow-up for the post-discharge medical visit, 2) time to and number of ER visits, 3) time to and total days of hospitalization. For example, time from discharge to first ER visit will be calculated for each subject and those who never have an ER visit will be censored at the end of study follow-up. Stratified Cox proportional hazards regression models will be fit with intervention group as the independent variable and discharge location (e.g. transplant unit, general unit) as a stratification factor, due to the potential for different underlying rates based on discharge location. The proportional hazards assumption will be checked using log-log plots of survival and Schoenfeld residuals.

For the primary outcome (self-efficacy for self-care at 12 months) a sample of 236 caregivers per arm allows for detection of an intervention group difference of similar magnitude as that found in our CRx trial (3.56 +/- 1.47 vs. 3.92 +/- 1.24). Calculations were performed under the following conditions: with nonparametric adjustment accounting for the fact that an ordinal logistic model with intervention group as the only covariate is equivalent to a Mann-Whitney U test; sample size calculation using a group allocation of 1:1; power=0.8; $\alpha=0.05$. We will therefore enroll 480 food insecure caregivers to accomplish Aim 1. With this sample size, power is sufficient to see at least a 0.26 standard deviation (SD) difference in Generalized Self-Efficacy between intervention and control groups. Assuming a standard deviation of about 5 (based on US adult population norms), a 0.26 SD difference would be equal to 1.3 points.

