We will use the analytic approach described for Aim 1, following the principles of intent-to-treat. Here, we discuss analytic issues unique to Aim 2. To facilitate ease of interpretation of the primary outcome, we will linearly rescale the composite score for the Child HCAHPS dimension of satisfaction with discharge.⁵⁹ Three possible responses for each of the five items included in this dimension will be scored as: No=1; Yes, somewhat=2; Yes, definitely=3. Scores will be transformed using the formula: $y = 100 * (x-a)/(b-a)$ where y=the transformed score, x=the original score, a=the minimum possible score and b=the maximum possible score. Transformed items will be averaged to generate the composite score (range 0-100, higher values mean greater satisfaction). Of particular interest for the non-inferiority hypothesis (H2a) will be the confidence interval for the difference (usual care - CRx-H) and whether or not the upper limit of the confidence interval exceeds the non-inferiority margin. Of note, superiority of the intervention with respect to satisfaction with care, child and caregiver health, and stigma will also be tested as this can be done without penalty. Caregiver satisfaction will be measured at 7 days post discharge and will reference the index hospitalization; no longitudinal analyses will be conducted for this outcome. Typically, analyses of HCAHPS data adjust for case-mix (age, education and general health status); this will be feasible, but given the randomized design and single-site analysis, adjustment should not necessary. To determine whether there are substantial differences in the intervention's effect on food insecure compared to food secure caregivers, the intervention by food security status interaction will be tested. As in Aim 1, we will examine for differential intervention effects on primary and secondary outcomes among racial and ethnic groups, and by sex, using effect modification analyses. Some analyses will be restricted to the food secure group (N=160) to provide a more complete assessment of the impact of the intervention on this group (e.g., changes in knowledge and attitudes about food insecurity and changes in food security over time).

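### The Aim 2 non-inferiority interval leaves out the food security stratum used in randomisation: a slightly conservative omission that costs nothing to mend

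*SAP*

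**What the plan says.** Under the RCT strategy, the SAP states: "To ensure balance of intervention groups by food security status, we will use stratified randomization to allocate subjects to usual care or CRx-H". Permuted blocks are used within each stratum, with accrual goals of 480 food insecure and 160 food secure caregivers. The stratum is known before randomisation: "Food security status will be measured during the study screening process".

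The Aim 2 analysis section takes all 640 caregivers and carries over the Aim 1 approach. The primary outcome is the rescaled Child HCAHPS discharge composite at 7 days, and the decision rests on one interval: "Of particular interest for the non-inferiority hypothesis (H2a) will be the confidence interval for the difference", usual care minus CRx-H, with its upper limit compared with the margin. No covariate is named for it. Three other statements bear on the point:

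- The Aim 1 covariate rule: "If there is a serious imbalance in baseline covariates despite randomization, those covariates will be included in the model".
- On HCAHPS case-mix adjustment for age, education and general health: "given the randomized design and single-site analysis, adjustment should not necessary".
- On whether the effect differs by food security: "the intervention by food security status interaction will be tested".

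The SAP also plans some analyses in the food secure group alone. Its examples are knowledge, attitudes and food security over time; satisfaction is not among them, though the list is open. The protocol's Statistical Plan (section C of the full-trial version) adds descriptive summaries, intent-to-treat, and further a priori analyses as needed.

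**The concern.** When randomisation is stratified, the arms are balanced on the stratum by design, so any difference in mean outcome between strata does not enter the variance of the treatment difference. An analysis without the stratum still counts that between-stratum spread as noise. The standard error it reports is then larger than the true one, and a non-inferiority test based on it is harder to pass than its nominal level implies.

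Nothing in the SAP brings the stratum in. The Aim 1 rule is triggered by imbalance, which is what the blocks prevent here. The case-mix remark concerns other variables and points away from adjustment. The interaction model would normally carry a food security main effect, but the SAP does not say that this model supplies the H2a interval.

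A smaller matter sits beside this. The interaction test is the planned check on whether the pooled conclusion suits both groups. The SAP does not say that satisfaction differences and intervals will be shown by stratum, or how the interaction result bears on H2a. If the test has little power, a non-significant result alone tells the reader little.

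**Working it through.** **Inputs from the SAP.** 640 caregivers, 1:1, so 320 per arm; 240 food insecure and 80 food secure per arm (weights 0.75 and 0.25); margin 1.6; SD 8; α = 0.05; power 0.8. Sidedness and confidence level are not stated, so one-sided 5% (z = 1.645) and 2.5% (z = 1.96) are both shown. Full response is assumed.

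**Assumption.** The gap g in mean satisfaction between strata is not given in the documents; g = 2, 4 and 6 points are used. The SAP takes SD 8 from an adult HCAHPS study and does not say whether it is a within-stratum or a total SD, so both readings are shown.

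**Step 1: the plan's own figure.** SE = 8 × √(2/320) = 0.632. Power at no true difference = Φ(1.6/0.632 − 1.645) = 81.2%. The SAP's 80% reproduces at one-sided 5%. At 2.5% it is Φ(1.6/0.632 − 1.96) = 71.6%.

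**Step 2: excess width.** The between-stratum variance is 0.75 × 0.25 × g² = 0.1875g², which gives 0.75, 3.00 and 6.75.

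- SD 8 within stratum: r = √((64 + 0.1875g²)/64) = 1.006, 1.023, 1.051.
- SD 8 total: r = √(64/(64 − 0.1875g²)) = 1.006, 1.024, 1.057.

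**Step 3: power at no true difference.** Let SE_w be the standard error from the within-stratum SD. Adjusted power is Φ(1.6/SE_w − z); unadjusted power is Φ(1.6/SE_w − z·r). When SD 8 is the total, the within-stratum SD is √(64 − 0.1875g²) = 7.953, 7.810, 7.566, and SE_w = 0.629, 0.617, 0.598.

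| Reading of SD 8 | One-sided level | Unadjusted, g = 2 / 4 / 6 | Adjusted, g = 2 / 4 / 6 |
|---|---|---|---|
| Total | 5% | 81.3 / 81.8 / 82.5% | 81.6 / 82.8 / 84.8% |
| Within stratum | 5% | 80.9 / 80.1 / 78.8% | 81.2% throughout |
| Total | 2.5% | 71.7 / 72.0 / 72.7% | 72.1 / 73.6 / 76.3% |
| Within stratum | 2.5% | 71.2 / 70.0 / 68.0% | 71.6% throughout |

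At one-sided 5% the gain is about 0.3, 1.0 and 2.3 points on either reading.

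**Step 4: type I error at the margin.** Φ(−1.645·r), within-stratum reading: 4.9%, 4.6%, 4.2%, each below the nominal 5%.

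**Step 5: interaction test and stratum intervals, at SD 8 within stratum.**

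- Food insecure: SE = 8 × √(2/240) = 0.730; half-width 1.20 (90%) or 1.43 (95%).
- Food secure: SE = 8 × √(2/80) = 1.265; half-width 2.08 (90%) or 2.48 (95%).
- Interaction: SE = √(0.730² + 1.265²) = 1.461. The difference in effects detectable with 80% power at two-sided 5% is (1.96 + 0.84) × 1.461 ≈ 4.1 points. Power is 19% for a difference of 1.6 and 54% for 3.
- Non-inferiority power within the food secure stratum, at no true difference: Φ(1.6/1.265 − 1.645) = 35%, or 24% at one-sided 2.5%.

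**The case against.** The strongest reply is that the omission endangers no conclusion. The estimate is unbiased, the error rate is at or below nominal, and the gain rests on gaps that the documents do not supply. The only group difference in the SAP's sample size text is by race, 79.3 against 77.4, or 1.9 points; a food security gap of that size would widen the interval by about 0.5%. All of this stands, and it is why the point is minor. A reader might infer from the lower rows of the table that the plan falls short of its stated power. That inference needs SD 8 to be a within-stratum figure, which the SAP does not say. If SD 8 is the total, the unadjusted analysis still exceeds 81% at one-sided 5%.

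Heterogeneity is also already addressed. The interaction is prespecified, its model yields both stratum differences, and the SAP is looking for substantial differences, not ones the size of the margin. So no analysis is missing; what is unlisted is an output. The food secure interval would often be inconclusive too, since its half-width exceeds 1.6.

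A stronger reading is tempting: the trial enrols food insecure and food secure caregivers 75:25, the recruitment projection implies 43:57 (1023 to 1357), and so the pooled test might seem to answer the wrong question for a universal intervention. The documents do not support calling this a defect. The SAP sets the 480:160 split deliberately and defines the Aim 2 population as all enrolled caregivers, and the pooled test is correct for that mix. Weighting matters only if the effect differs by stratum, which no passage suggests, and the consequence could then run in either direction. Standardising to 43:57 would cut power from 81% to 65%.

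Nor does the Cox model wording, "discharge location (e.g. transplant unit, general unit) as a stratification factor", show that food security was left out on purpose. Discharge location there separates baseline hazards; it is not the randomisation factor.

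**Conclusion.** The point holds as a small, free improvement. The Aim 2 primary interval does not name the randomisation stratum, and the inherited covariate rule would not bring it in. The interval is too wide by about 0.6%, 2% or 5 to 6% for assumed stratum gaps of 2, 4 or 6 points, in the conservative direction. The result rests on the assumed gaps, on full response, and on randomisation being stratified as the SAP describes; the protocol has REDCap randomise after food security screening and does not restate the strata. With no gap between strata there is nothing to gain and nothing lost.

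The lack of a commitment to stratum-specific satisfaction intervals is a reporting detail. It is worth settling because the interaction test is informative only for differences in effect of around 4 points or more.

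**What to change.** 1. In the Aim 2 analysis section, state that the satisfaction model supplying the H2a interval includes food security status at screening, the randomisation stratum, as a covariate whether or not imbalance is seen. Keep the pooled test and the 1.6-point margin as they are.
2. As a supporting result, report the satisfaction difference and interval in each stratum from the planned interaction model, beside the interaction test. Say that these intervals describe the remaining uncertainty and do not gate the H2a conclusion.

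The cost is a few sentences of SAP wording. The stratum is measured at screening, so the covariate needs no new data and no extra participants. The one thing to prepare readers for is the width of the food secure interval (half-width 2.1 points at 90%, 2.5 at 95%), which will often cross the margin even when there is no true difference.
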